# 7.2 **Optional Study**

# 7.2.1 Study Design for Ancillary Study

As part of the ACCL0934 trial, an ancillary study will examine the association between receipt of prophylactic levofloxacin and colonization or infection with antimicrobial-resistant organisms. Stool or peri-rectal swabs will be collected for assessment of longitudinal changes in colonization including several clinically significant bacterial organisms (*E. coli, K. pneumoniae, P. aeruginosa,* and *S. mitis*) and evaluation for the presence of resistance for each of these organisms to levofloxacin and other commonly used antibiotics in pediatric oncology. In addition to screening for specific antibiotic resistance among the aforementioned organisms, screening for the presence of any carbapenem-resistant Enterobacteriaceae will also be performed on specimens collected at the end of each patient's reporting period (i.e. their second stool or perirectal swab).

All patients enrolled on ACCL0934 will be offered the opportunity to participate in this ancillary resistance study. Colonization of resistant organisms will be determined by either peri-rectal or stool swabs. In comparison to stool specimens, peri-rectal swabs are 90% sensitive and 100% specific in identifying the presence of fluoroquinolone resistant *E. coli.* Consequently, peri-rectal swabs will be the preferred method of resistance surveillance although an institution and/or patient may choose to use stool specimens as long as the method of collection is constant within an individual patient. If a stool specimen is chosen as the method of collection, but cannot be provided during a sampling period (for example, in the event of constipation), then a peri-rectal swab may be substituted.

Stool specimens or peri-rectal swabs will be obtained at baseline and then at the time of resolution of neutropenia for each of the study cycles (twice for those with AL and once for those undergoing HSCT). Sample collection will be obtained within 1 week of count recovery defined as an ANC  $> 200/\mu$ L following the nadir. If a patient does not resolve their neutropenia, then the specimen should be obtained on Day 60 from the start of the infection observation period or within 2 days before the next chemotherapy cycle is initiated, whichever comes first. Figure 1 displays the planned specimen collection schema. Patients with AL will be followed for 2 cycles of chemotherapy resulting in 3 stool or peri-rectal specimens and those patients undergoing HSCT will be followed for 1 transplant procedure resulting in 2 stool or peri-rectal specimens.

[figure not shown]

Figure 1. Peri-rectal or stool specimen collection schema

## 7.3 **Follow-up**

See Section 7.1.3 for required musculoskeletal assessment follow-up.

# 8.0 CRITERIA FOR REMOVAL FROM PROTOCOL THERAPY AND OFF STUDY CRITERIA

# 8.1 Criteria for Removal from Protocol Therapy

- a) Signs or symptoms suggestive of tendonitis or tendon rupture.
- b) Refusal of further protocol therapy by patient/parent/guardian.

\* Defined as ANC > 200/ $\mu$ L and rising post-nadir or Day 60 (from Day 1 of each cycle of systemic chemotherapy or HSCT Day +60) if an ANC > 200/ $\mu$ L has not been reached. For patients who begin their next cycle of chemotherapy before the ANC > 200/ $\mu$ L and before Day 60, the swab should be obtained prior to the first day of the next course of chemotherapy.

\*\*Baseline swabs can be performed anytime between the date of enrollment and Day 3 of chemotherapy for leukemia patients or Day -2 for HSCT recipients.

- c) Completion of planned study treatment.
- d) Physician determines it is in patient's best interest.

Patients who are off protocol therapy are to be followed until they meet the criteria for Off Study (see below). Follow-up data will be required unless consent was withdrawn.

## 8.2 Off Study Criteria

- a) Completion of study (12-month follow-up period evaluation).
- b) Death.
- c) Lost to follow-up.
- d) Withdrawal of consent for any further data submission.

#### 9.0 STATISTICAL CONSIDERATIONS

## 9.1 Statistical Design

This study is a randomized trial to investigate the effect of levofloxacin on preventing bacteremia in children being treated for AL or undergoing HSCT. Patients will be randomized between levofloxacin and no levofloxacin during 2 consecutive cycles of chemotherapy for AL or during 1 HSCT. Randomization will be stratified by 4 groups: 1) *de novo*, secondary or relapsed AML or acute leukemia of ambiguous lineage treated with standard AML therapy; 2) relapsed ALL; 3) autologous stem cell transplantation; 4) allogeneic stem cell transplantation. The study is designed to analyze AL and HSCT patients separately.

The primary aim is to determine the effect of levofloxacin on the incidence of bacteremia during the study timeframe of 2 cycles of chemotherapy or 1 transplant procedure among AL and HSCT subjects respectively. Besides assessing the safety of levofloxacin, especially on musculoskeletal disorders, other secondary aims are to determine the effect of levofloxacin on: total days of antibiotic administration, incidence of fever with neutropenia, incidence of severe infection, incidence of death from bacterial infection, incidence of CDAD, incidence of IFI, resistance patterns of bacterial isolates from sterile site cultures, evolution of antimicrobial resistance from stool or peri-rectal swab isolates of *E. coli, K. pneumoniae, P. aeruginosa* and S. *mitis* and presence of stool colonization by carbapenem-resistant Enterobacteriaceae.

## 9.2 Patient Accrual and Expected Duration of Trial

The study initially planned to enroll 532 eligible and evaluable children in total: 266 AL patients and 266 HSCT patients. Per Amendment #3, the sample size for HSCT patients is increased to 400. The study is designed to analyze AL and HSCT patient groups separately as it is important to know the effect of levofloxacin prophylaxis in each group. Taking into account up to 10% of enrolled patients being ineligible or inevaluable, the maximum study accrual per Amendment #3 is 740 patients: 296 AL patients and 444 HSCT patients.

COG enrollments on *de novo* and first relapse AML protocols have a combined estimate of 400 patients per year. Considering secondary and subsequent relapses, the number of AML patients potentially eligible for the study may go up to 450 per year. COG enrollments on first relapse ALL patients is at least 110 patients per year. Therefore, the AL patient pool should be at least 550 per year. As this study does not require concurrent enrollment to COG therapeutic protocols, the potential eligible AL patient pool should be even larger. As for HSCT patients, a recent COG randomized study ACCL0331 that investigated treatment of mucositis in HSCT patients enrolled about 110 HSCT patients per year. The

study initially projected to accrue 266 eligible and evaluable patients for each of AL and HSCT group in about 4 years. Amendment #3 increases the sample size for HSCT patients from 266 to 400. The recent accrual rate for HSCT patients on this study is slightly over 100 per year, which is higher than the previously projected 67 per year. Given the higher accrual rate, the accrual duration for HSCT patients will only be extended for approximately 6 months to achieve the increased sample size.

## 9.3 Statistical Analysis Methods

## 9.3.1 Endpoints

## 9.3.1.1 Primary Endpoint

The primary endpoint is occurrence of at least 1 episode of true bacteremia during the study timeframe of 2 cycles of chemotherapy or 1 transplant procedure among AL and HSCT subjects respectively. Similar to others, 49,50 positive cultures with common contaminants, namely coagulase negative *Staphylococcus*, *Corynebacterium* species, *Propionibacterium acnes*, *Bacillus* species, *Micrococcus* species, *Clostridium* species (except *C. septicum* and *C. perfringens*) and *Neisseria* species (except *N. gonorrhea* and *N. meningitides*), will require 2 positive blood cultures for the same organism within the same episode (irrespective of timing between the 2 or more cultures) or be associated with sepsis syndrome to be considered true bacteremia. We will use international consensus definitions for defining sepsis. 58-61 The observation period for infectious outcomes, including the primary endpoint will be the same for both arms irrespective of whether the child discontinues levofloxacin early for those allocated to that arm.

Specifically, the infection observation period will begin Day 3 of each cycle of chemotherapy and will end when the ANC is  $> 200/\mu L$  and rising post nadir, or at Day 60 if an ANC of  $> 200/\mu L$  has not been reached or Day 1 of the next cycle of chemotherapy, whichever occurs first. For patients undergoing HSCT, the observation period will begin on Day -2 from stem cell infusion and end when the ANC is  $> 200/\mu L$  and rising post nadir, or at Day 60 if an ANC  $> 200/\mu L$  has not been reached or the first day of subsequent cancer therapy, whichever occurs first.

Patients will be considered evaluable for the primary endpoint if data on bacteremia during the infection observation period are available, regardless of protocol treatment compliance.

#### 9.3.1.2 Secondary Endpoints

Stool surveillance testing will investigate for the following resistance patterns among stool commensals at the start and end day of each treatment period: the susceptibility of *E. coli, K. pneumoniae*, and *P. aeruginosa* stool or peri-rectal swab isolates to cefepime, imipenem and levofloxacin; the susceptibility of *S. mitis* peri-rectal swab isolates to cefepime, levofloxacin and penicillin. Additionally, the presence of carbapenem-resistant Enterobacteriaceae will be screened from each enrolled patient's second collected stool or peri-rectal swab. The trajectory of the resistance patterns for the gastrointestinal isolates colonizing each patient will then be evaluated. Data regarding the resistance patterns of bacterial isolates from all sterile site cultures will be described. In interpreting antimicrobial sensitivity testing of both gastrointestinal organisms and organisms isolated from sterile sites, an intermediate result will be considered resistant for analytic purposes.

A secondary endpoint will be the duration of parenteral antibiotic administration during the study timeframe of 2 cycles of chemotherapy or 1 transplant procedure. Each day of parenteral administration will be collected irrespective of the indication or type of antibiotic given and the observation timeframe will be the same as that described for the primary endpoint. Other secondary endpoints include the incidence of febrile neutropenia, severe infection and death from bacterial infection. Severe bloodstream bacterial, fungal, and clinically documented infections and death from bacterial infection will consist of episodes of infection that are graded as CTCAE version 4 Grades 4 or 5 respectively. Secondary

endpoints on musculoskeletal adverse events and particularly tendinopathy (tendonitis and tendon rupture) will be collected. CDAD will be defined as a positive *C. difficile* toxin assay result and diarrhea, CTCAE version 4, Grade 2 and higher. Microbiologically-proven IFIs will be recorded.

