#### 1.2.2

To determine the effect of levofloxacin prophylaxis on total number of days of antibiotic administration (prophylactic, empiric and treatment) in children undergoing therapy for AL and HSCT.

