For the secondary endpoint on total number of days of antibiotic administration, considering a 2-sample t-test, with about 133 AL patients per arm we will have 90% power to detect a difference of 0.4 SD between the 2 arms in the mean of the number of days of parenteral antibiotic administration at 2-sided alpha of 0.05; with about 200 HSCT patients per arm we will have 85% power to detect a difference of 0.3 SD between the 2 arms in the mean number of days of parenteral antibiotic administration. For the secondary endpoints on the incidence of febrile neutropenia, severe infection, and death from bacteremia, the observed incidence rate will be compared between the 2 randomized arms. The power of such secondary analyses depends on the baseline incidence and the difference in incidence between the 2 arms. For these secondary analyses, if, for example, we consider possible baseline incidence values of 40%, 30%, 20%, 15%, 10%, or 5% in the control arm, in AL group (about 133 patients per arm) we will have a power of 95%, 84%, 63%, 49%, 34%, or 19%, respectively, to detect a levofloxacin treatment effect if levofloxacin leads to a relative reduction of 50% in the corresponding baseline incidence rate (i.e., rate with levofloxacin of 20%, 15%, 10%, 7.5%, 5%, or 2.5% respectively); for HSCT group (about 200 patients per arm), the corresponding power for a 50% relative reduction in these baseline incidence rates will be 99%, 95%, 80%, 66%, 48%, and 26% respectively. The test considered is a Chi-square test with 2-sided alpha of 0.05. It can be seen that the power for detecting a treatment difference in these secondary analyses might be limited if the baseline incidence is rare.

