For the secondary endpoints, the total number of days of parenteral antibiotic administration will be compared between the 2 arms using 2-sample t-test. Wilcoxon rank sum test will also be considered. We will also use linear regression models to estimate any treatment difference in total days of parenteral antibiotic administration and adjust for randomization stratification and potentially other patient or treatment characteristics. The incidence of febrile neutropenia, severe infection from bacteremia, fatal infections from bacteremia and musculoskeletal adverse events will be compared between the 2 randomized arms similarly as the analyses on bacteremia. For the analysis on the incidence of tendon rupture, we will also consider separating levofloxacin patients into those with/without concurrent steroid use and comparing them separately to control patients, or adjusting for concurrent steroid use as covariate in logistic regression models. The incidence of CDAD and proven or probable IFIs will also be compared between the 2 study arms in a similar manner. A patient with multiple documented episodes of CDAD or proven or probable IFI will only be counted once when calculating the binary incidence rates. For these secondary endpoints, appropriate regression models that combine AL and HSCT patients will be performed to evaluate the treatment effect with levofloxacin in the two patient groups; test for interaction between treatment and patient group will be performed to examine if the effect of levofloxacin on these secondary endpoints differs between the two patient groups.

Factors that can potentially confound the true association of the randomized exposure (levofloxacin) with the primary and two of the secondary outcome measures (1.2.1 and 1.2.2) will be compared across the two randomization arms to assure a balanced distribution. These include the use of antibiotic or ethanol as dwells or locks in central venous catheters (CVC) to reduce CVC infections and the use of chlorhexidine gluconate baths to reduce CVC infections. Analyses adjusting for these factors will be exploratory in nature.

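### Objective 1.2.2 is total antibiotic days including prophylaxis, but the plan defines, powers and tests parenteral days only, so oral levofloxacin days are never counted

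*Combined protocol and SAP*

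**What the plan says.** Objective 1.2.2 is the effect of prophylaxis on the "total number of days of antibiotic administration (prophylactic, empiric and treatment"). No route is excluded, and prophylaxis is named first. Section 9.1 restates the aim as "total days of antibiotic administration".

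The endpoint in 9.3.1.2 is narrower: "A secondary endpoint will be the duration of parenteral antibiotic administration during the study timeframe". Its counting rule is "Each day of parenteral administration will be collected irrespective of the indication or type of antibiotic given".

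Section 9.3.2 opens with the broad label, "For the secondary endpoint on total number of days of antibiotic administration, considering a 2-sample t-test", but the quantity it powers for AL is a "difference of 0.4 SD between the 2 arms in the mean of the number of days of parenteral antibiotic administration". The HSCT statement (0.3 SD) also concerns parenteral days.

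In 9.3.3, "the total number of days of parenteral antibiotic administration will be compared between the 2 arms", and the linear regression has the same outcome. The same section lists "the primary and two of the secondary outcome measures (1.2.1 and 1.2.2") as outcomes for which confounder balance will be checked, so 1.2.2 is treated as an outcome under analysis.

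**The concern.** Apart from PCP prophylaxis, levofloxacin in Arm B is the only antibacterial prophylaxis that section 4.1.2 allows. Section 4.2 makes the oral route the default and IV the fallback. The endpoint therefore omits the usual form of the exposure that 1.2.2 names. By the plain wording of 9.3.1.2, a levofloxacin day counts if the drug is infused and not if it is swallowed. The Arm B count then depends on oral tolerance and is neither total exposure nor purely empiric and treatment use.

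What is at stake is the direction of the conclusion. A fall in parenteral days could be presented under 1.2.2 as a saving in antibiotic days when total exposure had risen. The trial's stated purpose is to weigh the benefit of prophylaxis against risks that include resistance, so that distinction matters.

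**Working it through.** **The plan's own figures.** Two-sample t-test, two-sided alpha 0.05, from 9.3.2. Normal approximation: power = Φ(d·√(n/2) − 1.96), with d the difference in SD units and n the number per arm.

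- AL: n = 133, d = 0.4. 0.4 × √66.5 = 3.262; 3.262 − 1.96 = 1.302; power 90.4% (90.1% with the t distribution). Stated: 90%.
- HSCT: n = 200, d = 0.3. 0.3 × √100 = 3.000; 3.000 − 1.96 = 1.040; power 85.1% (84.9% with the t distribution). Stated: 85%.

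The arithmetic is right. The variable is parenteral days.

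**Window length.** Under 4.1.1 and 7.1.2, the levofloxacin period and the infection observation period start on the same day and end by nearly the same rules. The upper limits are:

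- AL, Day 3 to Day 60: 60 − 3 + 1 = 58 days per cycle, 116 over two cycles.
- HSCT, Day −2 to Day +60: 60 − (−2) + 1 = 63 days.

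**The two measures.** Let W be the window in days, and P_A and P_B the days of parenteral antibiotics other than study drug in each arm. Section 4.1.1 holds levofloxacin during such therapy and restarts it afterwards while the window is open. With full adherence, levofloxacin days are W − P_B. Then:

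- total days, Arm B = P_B + (W − P_B) = W
- total days, Arm A = P_A
- total-days difference, B minus A = W − P_A, which cannot be negative
- written endpoint with all levofloxacin oral, B minus A = P_B − P_A, which may be negative

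Assumptions: equal W in both arms, no oral antibacterial other than levofloxacin, PCP prophylaxis not counted, and whole days counted.

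**Illustration, not a prediction.** P_A = 14 is borrowed from the example of an empiric course in 4.1.1. W = 14, 20 and 28 are assumed; 58 and 63 are the limits above.

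| W | Total days, B minus A |
|---|---|
| 14 | 0 |
| 20 | +6 |
| 28 | +14 |
| 58 | +44 |
| 63 | +49 |

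Over the same cases the written endpoint shows 0, −7 or −14 days for P_B = 14, 7 or 0.

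**Incomplete adherence.** If levofloxacin is taken on a share a of eligible days, Arm B's total is P_B + a(W − P_B). It exceeds P_A when a > (P_A − P_B)/(W − P_B). With P_A = 14:

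| W | Threshold, P_B = 0 | Threshold, P_B = 7 |
|---|---|---|
| 20 | 14/20 = 0.70 | 7/13 = 0.54 |
| 28 | 14/28 = 0.50 | 7/21 = 0.33 |
| 58 | 14/58 = 0.24 | 7/51 = 0.14 |
| 63 | 14/63 = 0.22 | 7/56 = 0.13 |

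The reversal does not need full adherence.

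**Is total exposure analysed elsewhere?** Section 9.5.2 compares antibiotic days and class between arms but excludes the study drug. Section 9.5.2.1 describes broad-spectrum use on top of levofloxacin. Neither yields total days with study drug included.

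**The case against.** Section 9.3 is internally consistent in what it defines, powers and tests. Rewording 1.2.2, 9.1 and the opening of the power paragraph to parenteral days would remove the contradiction. It would also drop a question the sponsor asked and collects the data to answer, so it is the weaker remedy.

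With full adherence the total-days comparison largely reflects assignment to a daily drug, so its sign is close to built in. That stands as a caution: the size of the difference and its confidence interval will tell more than the p-value. It does not justify leaving the quantity unreported.

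A result published under the name used in 9.3.3 would not itself claim a saving in total exposure. That is true, but 9.3.2 gives the parenteral measure the total-days label, and no other analysis serves 1.2.2.

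Catheter locks given as bacteremia prophylaxis are also allowed and recorded, so levofloxacin is not the only preventive antibiotic in the trial. Locks are not systemic therapy and do not alter the count.

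Whether IV levofloxacin counts is open to argument. The notes to the therapy delivery maps treat parenteral antibiotics for other indications as a category apart from levofloxacin. The plain wording of 9.3.1.2 includes it, but the plan should say so.

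The illustrative figures carry no weight as estimates. The largest pair a maximum window with a single 14-day course, and the AL figures are per cycle although the endpoint spans two.

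**Conclusion.** The concern holds. Followed exactly, the plan does not answer 1.2.2 as worded; it tests only the parenteral part. Confidence in the mismatch is high, because it can be read directly from the text. The possible reversal of direction follows from the hold-and-restart rule and the shared window, under the assumptions listed. Its size cannot be estimated, because the documents give no typical window, antibiotic days or oral/IV split.

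The 90% and 85% power figures are correct for parenteral days and say nothing in days about total exposure. The effect is confined to one secondary objective; the primary analysis and sample size are untouched. It should be corrected.

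**What to change.** - In 9.3.1.2 and 9.3.3, add as the analysis of 1.2.2 an intention-to-treat comparison, separately for AL and HSCT, of total systemic antibacterial days by any route, protocol levofloxacin included. State how PCP prophylaxis is handled, identically in both arms.
- Keep the parenteral-days endpoint and state explicitly that IV levofloxacin days count under its rule. A sensitivity analysis excluding study drug is optional.
- In 9.3.2, label the 0.4 SD and 0.3 SD statements, including the opening phrase, as applying to parenteral days.
- Report the two results side by side.

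The cost is wording and one extra analysis per cohort. No new data are needed: section 7.1.2.1 already records study-drug days and the names and dates of oral and parenteral antibacterials. The price is that total days will probably look less favourable to levofloxacin than parenteral days.

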## 4.0 TREATMENT PLAN

## 4.1 **Overview of Treatment plan**

Timing of protocol therapy administration, response assessment studies, and surgical interventions are based on schedules derived from the experimental design or on established standards of care. Minor unavoidable departures (up to 72 hours) from protocol directed therapy and/or disease evaluations (and up to 1 week for surgery) for valid clinical, patient and family logistical, or facility, procedure and/or anesthesia scheduling issues are acceptable per COG administrative Policy 5.14 (except where explicitly prohibited within the protocol).

In this study, patients will be randomized to no levofloxacin (Arm A) or levofloxacin (Arm B) at time of enrollment. Patients in Arm A receive no protocol treatment. Patients in Arm B receive levofloxacin as detailed below.

The required observations and adverse event reporting are identical in the two arms. See Section 7 for required observations and Section 11 for Adverse Event reporting.

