## Patients Undergoing HSCT

For children undergoing HSCT and assigned to Arm B, prophylaxis will be administered during 1 transplant procedure; levofloxacin will start on Day -2 from stem cell infusion.

For patients with AL and those undergoing HSCT, levofloxacin treatment will continue until one of the following is met, whichever occurs first:

- 1) ANC is  $> 200/\mu L$  and rising post-nadir OR
- 2) Day 60 (from Day 1 of each cycle of systemic chemotherapy or HSCT Day +60) if  $ANC > 200/\mu L$  is not reached OR
- 3) The day prior to the next cycle of chemotherapy OR
- 4) Patient meets criteria for removal from protocol therapy per Section 8.1.

For patients with AL receiving 2 courses of levofloxacin treatment, the first course of levofloxacin treatment will be discontinued when the patient meets the above criteria; unless the patient is off protocol, the second course of levofloxacin treatment will start on Day 3 of the next chemotherapy cycle. Patients who begin their second cycle of chemotherapy before the ANC >  $200/\mu L$  and before Day 60 (for Cycle 1) should continue levofloxacin treatment until the ANC is >  $200/\mu L$  and rising post nadir or they reach 60 days from Day 1 of the second cycle of chemotherapy.

For patients assigned to Arm B, levofloxacin will be held any time that parenteral antibacterial therapy is initiated according to local supportive care standards (for example, empiric antibiotics initiated for febrile neutropenia). For patients who have not met criteria for removal from protocol therapy, levofloxacin should be re-started when parenteral antibiotics have been discontinued (for example, following completion of a 14-day course of empiric therapy for febrile neutropenia), if the ANC is still  $< 200/\mu L$ , if Day 60 has not yet been reached and the next cycle of chemotherapy has not been initiated. For HSCT patients who develop fever between the time of enrollment and Day -2 of

conditioning (for example fevers associated with ATG therapy) who are started on empiric antibiotic therapy according to institutional standards, levofloxacin should be started once these empiric antibiotics are discontinued or on Day -2 of conditioning, whichever occurs later. Levofloxacin may be stopped and re-started multiple times according to when other parenteral antibiotics are administered.

Levofloxacin should be discontinued immediately for any patient with confirmed tendinopathy (tendonitis or tendon rupture).

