#### 4.1.2 Prophylactic Therapy

Antibacterial prophylaxis other than for PCP prophylaxis and levofloxacin for those on Arm B will not be permitted.

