# 4.2 **Study Therapy**

## **Levofloxacin: PO\* or IV**

Age  $\geq 6$  months to  $\leq 5$  years: administer 10 mg/kg twice daily for a total of 20 mg/kg per day

Maximum: 250 mg per dose; 500 mg per day

Age  $\geq$  5 years: administer 10 mg/kg once daily

Maximum: 750 mg per day

\*The study medication will be given PO if tolerated. If PO is not tolerated, study medication will be given by IV with the same dose and schedule. The PO levofloxacin is preferably administered 1 hour before or 2 hours after a meal, but may be taken with food if better tolerated by the patient. Antacids containing magnesium or aluminum, as well as sucralfate, metal cations such as iron, multivitamin preparations with zinc, and didanosine oral solution should not be taken within 2 hours before or after PO levofloxacin administration.

For children/adolescents who choose to take tablets of levofloxacin, the dose should be rounded to the nearest multiple of 125 mg. Rounding 'down' is permitted as long as the delivered dose i≥ 90% of the calculated dose. Otherwise, the dose should be rounded 'up' to the next multiple of 125 mg. For children using the oral solution, doses should be rounded to the nearest 25 mg.

If vomiting occurs within 30 minutes of taking the dose, the dose may be repeated once. If a dose is missed, it should be taken immediately and only if there are at least 12 hours until the next scheduled dose.

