## 7.1.2.1 General Infection Information

Data to be collected during the infection observation period will include incidence of fever with neutropenia, days of neutropenia, use of granulocyte-colony stimulating factor (G-CSF) and corticosteroid exposure (categorized as no exposure, ≤ 5 sequential days of or > 5 sequential days of corticosteroid treatment), incidence of signs or symptoms of tendinopathy (tendonitis or tendon rupture), incidence of fever, days until first fever, days of anti-fungal therapy given, hospitalization days, days of trial medication use, use of chlorhexidine baths (yes or no), use of prophylactic CVL locks (ethanol or antibiotic locks for bacteremia prophylaxis) (yes or no) and the name and start/stop dates for any oral and parenteral antibacterial therapy. Incidence of sepsis and severe bacterial and fungal microbiologically documented infections and clinically documented infections (CTCAE version 4, Grade 4 and Grade 5) will be recorded. For patients who die during the infection observation period and who have an autopsy performed, the report of the autopsy will be requested.

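### The tested parenteral-antibiotic-day endpoint does not exclude IV study levofloxacin, so the Arm B count depends on the route of the randomized drug

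*Combined protocol and SAP*

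**What the plan says.** Objective 1.2.2 asks how levofloxacin prophylaxis affects the total number of antibiotic days, and it names prophylactic, empiric and treatment use. Section 9.3.1.2 turns this into a duration of parenteral administration over the study timeframe: "Each day of parenteral administration will be collected irrespective of the indication or type of antibiotic given". Section 9.3.3 compares that total between arms by a two-sample t-test, with a Wilcoxon test and linear regression also foreseen. Section 9.3.2 gives its power: 90% for 0.4 SD in AL with about 133 patients per arm, and for HSCT, "with about 200 HSCT patients per arm we will have 85% power to detect a difference of 0.3 SD between the 2 arms".

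Four other provisions decide what enters the count:

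- Section 4.2 on the study drug: "If PO is not tolerated, study medication will be given by IV with the same dose and schedule".
- Section 4.1 on the control arm: "Patients in Arm A receive no protocol treatment".
- Section 4.1.2: "Antibacterial prophylaxis other than for PCP prophylaxis and levofloxacin for those on Arm B will not be permitted".
- Section 4.1.1 for Arm B: "levofloxacin will be held any time that parenteral antibacterial therapy is initiated according to local supportive care standards". Levofloxacin may be restarted once those antibiotics stop.

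On data, Section 7.1.2.1 collects days of trial medication and "the name and start/stop dates for any oral and parenteral antibacterial therapy".

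**The concern.** Read as written, the counting rule covers the study drug whenever it is given by IV. Only one arm can accrue such days, and they come from the intervention. Take four hypothetical children. An afebrile Arm B child with 15 days of oral levofloxacin scores 0. The same child, switched to IV because oral dosing is not tolerated, scores 15. An afebrile Arm A child scores 0. An Arm A child with 10 days of empiric IV therapy scores 10. The first two children have identical antibiotic exposure and identical infection histories, yet their scores differ by 15.

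Two sensible quantities could be targeted here, and the variable is neither. For total antibiotic exposure, oral prophylaxis should count as well. For the use of other parenteral antibiotics, IV prophylaxis should not count. What is at stake is the interpretation of a powered secondary endpoint. A null result could mean that prophylaxis did not reduce empiric and treatment use, or that it did and IV levofloxacin days filled the gap. If the rule stays unresolved in an open-label trial, two analysts could also derive different totals from the same data.

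**Working it through.** **Who can accrue the extra days.** Arm A receives no study drug, and no other antibacterial prophylaxis is allowed beyond PCP agents, which both arms may have. IV levofloxacin days can therefore fall only in Arm B.

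**Whether they overlap other counted days.** Levofloxacin stops when other parenteral antibacterials start. Overlap is limited to changeover days, on which a levofloxacin dose and the first dose of empiric therapy fall on the same date. Almost every IV levofloxacin day is therefore an additional counted day.

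**Reproducing the stated power (Section 9.3.2).** Inputs: n = 133 per arm with d = 0.4 SD (AL), and n = 200 per arm with d = 0.3 SD (HSCT). Two-sided alpha is 0.05, stated for AL and taken to be the same for HSCT. Power ≈ Φ(d/√(2/n) − 1.96).

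- AL: 0.4/√(2/133) = 3.26; Φ(1.30) = 0.904. The noncentral t gives 0.902. Stated: 90%.
- HSCT: 0.3/√(2/200) = 3.00; Φ(1.04) = 0.851. The noncentral t gives 0.849. Stated: 85%.

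Both figures reproduce.

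**Effect of counting IV levofloxacin.** Suppose non-study parenteral days fall in Arm B by the planned d, and IV levofloxacin raises the Arm B mean by m (in SD units, averaged over all Arm B patients). The measured difference is d − m, and the power to show a reduction is Φ((d − m)/√(2/n) − 1.96). The SD is held constant.

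| m (SD) | AL, d = 0.4 | HSCT, d = 0.3 |
|---|---|---|
| 0 | 90% | 85% |
| 0.05 | 81% | 71% |
| 0.1 | 69% | 52% |
| 0.2 | 37% | 17% |
| 0.3 | 13% | 2.5% (cancelled) |
| 0.4 | 2.5% (cancelled) | – |

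For example, AL at m = 0.1: 0.3/√(2/133) = 2.45; Φ(0.49) = 0.69. HSCT at m = 0.1: 0.2/√(2/200) = 2.00; Φ(0.04) = 0.52.

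**In days.** The documents do not give the SD or the share of patients dosed by IV, so the following are assumptions. With an SD of 5, 10 or 15 days, full cancellation needs an Arm B average of 2, 4 or 6 IV levofloxacin days in AL (0.4 × SD), or 1.5, 3 or 4.5 in HSCT (0.3 × SD). At SD 10, if 25% of Arm B receive IV levofloxacin for 4 days each, the average is 0.25 × 4 = 1 day, or 0.1 SD, which is the 69% and 52% row. At the same 25% share, cancellation would take 16 IV days per such patient in AL (4/0.25) or 12 in HSCT (3/0.25).

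The Wilcoxon test and the regression models use the same outcome, so they do not remove the shift. A larger sample would not remove it either.

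**The case against.** The strongest reply is that the count is deliberate. Objective 1.2.2 includes prophylactic days, and a rule that ignores indication fits that. On this view an IV levofloxacin day is a real antibiotic day caused by assignment, and the intent-to-treat difference is a valid contrast. This stands in part: the comparison cannot be called biased without naming a target. It does not rescue the variable, because an endpoint meant to include prophylaxis would have to count it by mouth too.

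The literal reading can also be questioned. Section 7.1.2.1 lists trial medication separately from other antibacterial therapy, and the hold rule in Section 4.1.1 must use its term to mean drugs other than levofloxacin, or the drug would trigger its own hold. The authors may therefore have meant to leave it out. But Section 9.3.1.2 does not say so, whereas the ancillary study (Section 9.5.2) explicitly sets the study drug aside when describing other antibiotic exposure. That separation, and the description by class in Section 9.5.2.1, serve the resistance analyses and do not redefine this endpoint.

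Two further limits are fair. Section 9.3.2 powers a two-sided difference and names no direction, so a reduction is only the benefit direction of that test. And where febrile neutropenia is common, as Section 2.1 reports, the hold rule leaves less time in which IV levofloxacin could be given.

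**Conclusion.** The point holds as a flaw in the definition of a secondary endpoint. Followed as written, the tested variable scores identical prophylaxis as zero by mouth and one per day by IV. It matches neither objective 1.2.2 nor non-study parenteral use, and as a measure of the latter it is shifted against levofloxacin.

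The direction of the shift follows from the text. Its size does not. The power losses depend on an assumed mean of IV levofloxacin days, on a true reduction equal to the planned difference, and on a constant SD.

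A reader might infer more: that the endpoint is biased whatever its target, that any benefit will be cancelled, or that the stated power is wrong. The documents support none of these. The first depends on which quantity is meant. The second needs average IV use of 0.4 SD (AL) or 0.3 SD (HSCT), and nothing in the documents shows that; modest use would erode power without removing it. The third fails because 90% and 85% reproduce.

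**What to change.** In Sections 9.3.1.2 and 9.3.3, define the tested endpoint as days of parenteral antibacterial therapy other than protocol levofloxacin, derived from the drug names, start/stop dates and trial-medication days already collected. Any levofloxacin given outside the protocol as treatment would still count. Keep the current all-parenteral count as a supportive analysis. For objective 1.2.2, report total antibiotic days separately, by all routes and including protocol levofloxacin. Settle this before arm-level totals are compared.

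The cost is wording in two sections and one or two more derived lines in the tables. One item needs confirmation: Section 7.1.2.1 does not name the route of trial medication, and the administration logs in the therapy delivery maps show dates and doses but no route column. Levofloxacin days by route should be reported only if the forms capture route, and the all-parenteral count needs the same information. The proposed tested endpoint does not, because it leaves out protocol levofloxacin whatever its route. No dose, schedule or clinical rule changes.
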